STUDY PROTOCOL PLAN AND STADISTICAL ANALYSIS PLAN (SAP)

UNIVERSITY CEU CARDENAL HERRERA

Principal investigator: [name] [name]

**TITLE: Analysis, Comparison and Evaluation of Cervical Range of Motion and Neck Pain After Deep Dry Needling and Superficial Dry Needling in the Upper Trapezius:
A Randomised Controlled Trial**

Research and Ethics Committee of CEU Cardenal Herrera University Number: CEI15/006

NCT ID (not yet assigned)

DATE: 12-4-2015

STUDY PROTOCOL PLAN

Objectives:

The objectives of our study have been the following:

General:

- Analyze, compare and evaluate changes in cervical range of motion and pain threshold pressure in the neck after performing the deep dry needling technique (DDN), the superficial dry needling technique (SDN) and a simulated dry needling technique in the gastrocnemius muscle (control group).

Specific:

- To evaluate the changes in the cervical range of motion (CROM) in homolateral and contralateral rotation, ipsilateral and contralateral inclination, flexion and extension at the cervical level. Myofascial trigger point (MTP) 1 of the upper trapezius.
- Determine changes in pain intensity after superficial dry needling technique (SDN) and deep dry needling (DDN).
- To compare the results of the technique of superficial dry needling (SDN), deep dry needling (DDN) and a simulated dry needling technique in the gastrocnemius muscle (control group).

Volunteers who want to participate in the study will read the general information of the study and sign the informed consent to participate in the study.

Once the informed consent has been read and delivered, the evaluator will check that they meet the inclusion criteria. After the data collection, a randomization (Epidat V4.0) of the selected subjects will be carried out to assign them to one of the intervention groups.

In the evaluation room, the evaluator, after taking the measurements of weight and height, will ask the subject to sit correctly on the chair, proceeding to locate the Myofascial trigger point (MTP) 1 of the upper trapezius, both right and left.

To locate the MTP 1, the palpation technique will be used, grasping the belly of the muscle between the thumb and the 2nd and 3rd fingers. The evaluator will press the fibers with a forward and backward movement to find the taut bands. Once the taut band is found longitudinally, the nodule and the point of greatest sensitivity to pressure will be located.

Once the MTP 1 is located, it will be marked with a dermal marker. Those subjects in whom the MTP 1 can not be located with precision, will be excluded from the study.

After having marked the MTP 1, the evaluator will make the subject the algometry in the MTP 1. 3 measurements will be taken with an interval of 20 seconds between measurement and measurement, and the average of the three measurements obtained will be calculated. After 5 minutes, the algometric measurement will be repeated to calculate statistically the error of the device in our study.

Next, the goniometer will be placed on the subjects and they will be instructed to do a right rotation movement, left rotation, right lateral flexion, left lateral flexion, flexion and extension with the back straight and hands placed on the thighs. Between movement and movement you will be asked to return to the starting position. After 5 minutes, the goniometric measurement sequence is repeated to calculate statistically the error of the device in our study.

Once the pre-intervention measurements have been made, the subject will go to the adjoining room to carry out the intervention.

The intervention sequence varied depending on the group to which the subject "Group intervention 1" (G1), "Group intervention 2" (G2) and "Control group" (G3) belonged. The subject will be instructed to remove the shirt and lie down on the stretcher in the prone position. After one minute, the intervenor will proceed to perform the intervention according to the intervention group:

- "Intervention group 1" (G1): the superficial dry needling technique will be performed with a duration of nine minutes in the upper trapezius.

Initial position: Patient lying in prone position without shirt and with a contralateral cervical rotation of the side to be treated. The auditor is placed in a sitting position on a stool at the head of the stretcher.

Placement of hands: The auditor locates MTP 1 of the upper trapezius in the clamp of the side to be treated and, between his index and middle fingers with the thumb, he takes the MTP 1.

Technique: The inspector, with gloves, disinfects the area to be treated with 70° alcohol. Once the alcohol is applied, the interventor places the needle in the MTP 1, with the guide tube resting on the skin of the patient. The interventor holds the guide tube between the index and middle fingers, tap the needle with the index finger of the other hand to insert the needle into the skin. Once the needle is inserted at the subcutaneous level, the auditor removes the guide tube and rotates the needle until resistance to rotation is felt. After waiting for three minutes, the controller returns to rotate the needle until he notices a new resistance stop. This sequence is repeated a total of three times (nine minutes). Once the three stimuli have been made, the interventor proceeds to withdraw the needle. Next, hemostasis is performed in the area. Once this hemostasis is completed, the patient is incorporated and dressed.

- "Intervention group 2" (G2): the deep dry needling technique will be performed with a duration of less than one minute in the upper trapezius.

Initial position: Patient lying in prone position without shirt and with a contralateral cervical rotation of the side to be treated. The auditor is placed in a sitting position on a stool at the head of the stretcher.

Placement of hands: The auditor locates the MTP 1 of the upper trapezius in the clamp of the side to be treated and, between his index and middle fingers with the thumb, he takes the MTP 1.

Technique: The inspector, with gloves, disinfects the area to be treated with 70° alcohol. Once the alcohol is applied, the interventor locates and takes the MTP 1

and places the needle in the MTP 1 with the guide tube resting on the skin of the patient. The inspector holds the guide tube between the index and middle fingers, lightly touch the needle with the index finger of the other hand to insert the needle perpendicularly into the skin, directing it towards the inspector's thumb. Once the needle is inserted subcutaneously, the guide tube is removed. The controller deepens the needle to MTP 1, and makes fast inputs and outputs into the MTP. The rapid exit is made to the subcutaneous cellular tissue, outside the muscle, but not outside the skin. Next, hemostasis is performed in the area. Once this hemostasis is completed, the patient is incorporated and dressed.

- "Control group (G3)": the simulated dry puncture technique will be performed in the gastrocnemius muscle.

Initial position: Patient in prone position on the stretcher, with his head placed in the hollow of the stretcher. The intervener is placed in front feint, on the homolateral side of the side to intervention.

Technique: The patient lies on the stretcher without the trousers. The interventor, with the guide tube, simulates the technique of puncture in the right twin of the subject. The controller cleans the area with 70° alcohol. Once the alcohol is applied, he performs the simulated puncture technique in a plane with his index and middle fingers with the guide tube. It is important that the subject has his head stuck in the hollow of the head of the stretcher throughout the technique to make a correct masking.

Next, a simulation of hemostasis is performed in the area. Once this simulation is finished, the patient is incorporated and dressed.

Once the intervention is done, the subject will return to the evaluation room to proceed to the evaluation immediately after the intervention (POSTINT), both algometric and goniometric. After these measurements, the subject will be summoned at the same time to return at 24 hours (POST24h), at 72 hours (POST72h) and at 7 days (POST7d) to perform the corresponding algometric and goniometric measurements.

This study will be carried out in two adjoining rooms, with a sufficient amplitude to offer freedom of movement, both to the evaluator and the auditor and the subject of the study.

In one of the rooms will be the evaluator to perform the measurements and collect the pre- and post-intervention values. In the adjoining room will be the controller, in charge of carrying out the corresponding intervention.

Between both rooms there are about eight meters of distance without steps or unevenness, and they will maintain an identical and constant temperature.

Statistical Analysis Plan (SAP)

To verify the correct randomization of the subjects to the intervention groups, a baseline homogeneity analysis of the pre-intervention response variables with the different explanatory variables will be performed. The statistical program that we will use will be SPSS v.20.

For the qualitative variables, double entry tables will be calculated and the Chi-Square test will be carried out (χ^2). For the quantitative variables, mean values and standard deviation (SD) will be calculated and a variance analysis procedure (ANOVA) will be applied.

The pre-intervention response variables will also be evaluated in the three intervention groups, to check their homogeneity and correct masking of the evaluator, applying ANOVA procedures.

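### Evaluator masking is checked only on pre-treatment values, while unequal needling times leave an arm cue at the first post-treatment measurement

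*Combined protocol and SAP*

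**What the plan says.** **Check of masking.** The closing paragraph of the Statistical Analysis Plan compares the outcome variables measured before treatment across the three groups by ANOVA. It gives this two purposes: to show homogeneity and to show that the evaluator was properly masked. No other check of evaluator masking is described.

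**Safeguards.** The study protocol plan puts the evaluator and the person who treats in two adjoining rooms about eight metres apart. In all three arms the subject is dressed again before going back. The evaluator collects the values both before and after treatment.

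**Timing.** For G1, "the superficial dry needling technique will be performed with a duration of nine minutes in the upper trapezius". For G2, "the deep dry needling technique will be performed with a duration of less than one minute in the upper trapezius". No duration is given for the simulated procedure in G3. One lead-in is common to all arms: "After one minute, the intervenor will proceed to perform the intervention according to the intervention group". The subject then returns directly for algometry and goniometry (POSTINT), with further measurements at 24 hours, 72 hours and 7 days.

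**Skin.** In G1 and G2 the person treating "disinfects the area to be treated with 70° alcohol", which is the upper trapezius, and after needling, "Next, hemostasis is performed in the area". In G3 the corresponding steps are at the calf: "The controller cleans the area with 70° alcohol" and "a simulation of hemostasis is performed in the area".

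**The concern.** The post-treatment measurements described are algometry and goniometry, and the evaluator takes both. If the evaluator can work out the arm before POSTINT, expectation can enter the readings. Detection bias of that kind cannot be removed afterwards by analysis.

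The check offered looks at the wrong moment. It uses data collected before the subject enters the treatment room, whereas the differences between arms that could give the arm away arise inside that room. The comparison would look the same whether or not the evaluator was unmasked by treatment. A non-significant result could then be reported as evidence of masking that it does not contain.

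**Working it through.** **1. The plan's own figure.** The G1 technique consists of three three-minute cycles: 3 × 3 = 9 minutes, as stated.

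**2. The time cue.**

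| | G1 | G2 | G3 |
|---|---|---|---|
| Common lead-in (min) | 1 | 1 | 1 |
| Procedure (min) | 9 | < 1 | not stated |
| Sum (min) | 10 | < 2 | unknown |

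The G1 v G2 gap is 9 minus less than 1, which is more than 8 minutes. The lead-in is the same in every arm and does not narrow it. Undressing, hemostasis and dressing come on top and are not timed. G3 cannot be placed on this scale.

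**3. Order of events and the check.** Baseline measurement comes first, then the move to the other room, then treatment, then POSTINT. A cue that arises during treatment cannot alter a value already recorded. The one exception is an arm known before baseline measurement. The protocol places randomisation after data collection but describes it ahead of the evaluation-room measurements, so the order is not fully settled. In that case the ANOVA might hint at biased baseline measurement. It still says nothing about unmasking that starts later.

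**4. Illustration of step 3.** This simulation rests on assumptions that are not in the documents: 20 or 40 subjects per arm, SD 1, pre-post correlation 0.7, two-sided 5% level, 4000 runs, no true treatment effect. A measurement bias was added to one arm after treatment only.

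| Bias (SD) | n per arm | Pre-treatment ANOVA rejects | Same ANOVA on post values rejects |
|---|---|---|---|
| 0 | 20 / 40 | 5.3% / 4.5% | 5.0% / 5.2% |
| 0.5 | 20 / 40 | 4.9% / 5.4% | 34% / 62% |
| 1.0 | 20 / 40 | 5.0% / 4.4% | 89% / 99.7% |

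The pre-treatment test stays near 5% whatever the bias. The right-hand column shows only what bias of an assumed size could do; it does not estimate bias in this trial. The logic does not depend on the chosen n, SD or correlation.

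**5. The skin cue.** Alcohol, puncture and hemostasis occur at the trapezius in G1 and G2 only. Against that, in every arm the evaluator has already palpated and marked the trigger point, taken three algometer readings there and repeated the algometry after five minutes. All subjects therefore return with a handled site. What differs between arms is narrower than handling as such, and its visibility is not documented.

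**The case against.** The best defence is that the plan does provide masking: separate rooms some distance apart, and subjects dressed before they return. Nothing says that the evaluator times absences or knows how long each technique lasts. The time cue separates G1 from G2 and bears on one of four post-treatment measurements. G3 may not be short, since control subjects also take off their trousers.

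Most of this stands as a limit on the claim. It does not remove the cue, because separate rooms and clothing do not hide how long a subject was away. It also does not rescue the check, which fails whatever the strength of the cues.

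Two stronger readings are tempting. A reader might infer that the skin gives the arm away because only the needled arms come back with a handled site. The documents do not support this: all arms return palpated, marked and pressed, and nothing says that a wipe, puncture or hemostasis is visible at POSTINT or that alcohol removes the mark. A reader might also want a percentage for how often the evaluator could identify the arm. That would need the variability of the untimed steps and a duration for G3, and neither is given.

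**Conclusion.** The concern holds in two parts.

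- **The masking check is wrong as written.** An ANOVA of pre-treatment values can describe baseline homogeneity and at most hint at biased baseline measurement. It cannot detect unmasking that begins with treatment. This follows from the order of events and needs no numerical assumption.
- **Time away is an available arm cue at POSTINT.** The supported size is a needling-time gap of more than eight minutes between G1 and G2, with G3 unknown. That it works as a cue assumes the evaluator notices the absence and knows roughly what each technique takes. Skin preparation at the trapezius may add a further cue, but that is a possibility only.

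It would go too far to conclude that the evaluator is unmasked or that the results will be biased. The documents do not show that unmasking occurs, and neither its probability nor the size of any bias in pain threshold or cervical motion can be computed from them. The changes are worth making because they are cheap and because the present check would give false assurance.

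**What to change.** 1. **Equalise time in the treatment room.** Set one total time for all arms, long enough to hold the nine-minute technique. Put any waiting before the procedure so that POSTINT still follows directly, and amend the common one-minute lead-in to match. Leave every technique, including the sham, unchanged.
2. **Relabel the ANOVA.** Keep it as a description of baseline homogeneity and delete the statement that it checks masking.
3. **Record a guess.** Once per subject, at a fixed and prespecified time, have the evaluator write down the arm they believe was given ('don't know' allowed) and the reason. Report the full table of guess by actual arm.
4. **Add a descriptive index.** For each arm, take the proportion of its own subjects guessed to be in that arm, minus the same proportion among the other subjects, with 'don't know' answers kept in the denominators. Its expected value is zero for an uninformed evaluator, whatever the guessing habit or allocation ratio. The plan states no sample size; with an assumed 20, 30 or 40 per arm and a guess rate of 1/3, the 95% half-width is 1.96 × √[(2/9)(1/n + 1/(2n))] = 0.25, 0.21 or 0.18. It should therefore not be treated as a formal test.

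**Cost.** Protocol wording, about eight extra minutes for G2 subjects (and for G3 if its procedure is short), and one recorded guess per subject. No extra staff or visits are needed.

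**Downsides.** The wait before the procedure will differ between arms and should be stated. A guess before POSTINT may draw the evaluator's attention to cues, while a guess after it may reflect the response just observed; the plan should choose one and say why. Needle marks may still be visible in G1 and G2.

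### The SAP states no between-arm analysis of the post-intervention data, so the trial's main comparison has no planned method and the baseline values enter no stated effect analysis

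*Combined protocol and SAP*

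**What the plan says.** **Objectives.** The general objective is to "Analyze, compare and evaluate changes in cervical range of motion and pain threshold pressure in the neck" after deep needling, superficial needling and a simulated control. The third specific objective repeats the three-way comparison.

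**Measurements.** Algometry and goniometry are done before the intervention, and each is repeated after five minutes to estimate device error. Both are then measured at four later points: POSTINT, POST24h, POST72h and POST7d.

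**SAP.** The first paragraph says that, to check the randomisation, "a baseline homogeneity analysis of the pre-intervention response variables with the different explanatory variables will be performed". The second paragraph assigns a chi-square test to qualitative variables and continues: "For the quantitative variables, mean values and standard deviation (SD) will be calculated and a variance analysis procedure (ANOVA) will be applied". The last paragraph says: "The pre-intervention response variables will also be evaluated in the three intervention groups", with ANOVA again, to check homogeneity and evaluator masking. Apart from naming the software, that is the whole SAP, and no redaction is marked in it.

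**The concern.** The comparison that the trial exists to make has no method attached to it. The outcome, visit, model, contrasts and significance rule would all have to be chosen outside the plan, possibly after the data have been seen. A reader could not then check the reported result against a pre-specified analysis.

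A second loss goes with it. Good pre-intervention values are collected for every outcome, but the plan uses them only for balance and masking checks and, through the five-minute repeats, for device error. They could make the arm comparison more precise at almost no cost.

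**Working it through.** The plan states no figure that could be reproduced. The check is a reading of the text, followed by illustrations on assumed values.

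**1. Objectives against SAP.**

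| Needed for the stated comparison | In the SAP |
|---|---|
| Post-intervention visits | None of the four is named |
| Outcome and primary visit | Not named |
| Contrasts between arms | Three groups are named only for pre-intervention variables |
| Use of baseline in an effect analysis | None stated |
| Estimates with confidence intervals | None stated |
| Alpha or multiplicity rule | None stated |

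**2. How many results are left open.** The first specific objective lists six movements: "homolateral and contralateral rotation, ipsilateral and contralateral inclination, flexion and extension at the cervical level". Pressure pain threshold adds one outcome, or two if algometry is done on both sides. The trigger point is located on both, but the text does not say how many sides are measured.

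- One side: (6 + 1) × 4 visits = 28.
- Two sides: (6 + 2) × 4 visits = 32.

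**3. Error rate, only if the ANOVA sentence is extended to outcomes.** Assume each test is made at 0.05 and there is no true effect.

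- Independent tests: 1 − 0.95^28 = 0.762; 1 − 0.95^32 = 0.806.
- Correlated tests, by simulation (assumed outcome correlation 0.3 to 0.5, visit correlation 0.6 to 0.8, 20 to 50 per arm): about 46% to 63% for 28 tests and 49% to 68% for 32.

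**4. Value of the baseline.** Assume one arm differs from the other two by 0.5 SD, a 2-df F test at 5%, n per arm, and baseline-to-follow-up correlation ρ. The group means are (0, 0, 0.5), so their mean is 1/6 and the sum of squared deviations is 2 × (1/6)² + (1/3)² = 1/6. The noncentrality is n / (6V), where V is the error variance relative to post-only ANOVA:

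- post-only: V = 1
- change score: V = 2(1 − ρ)
- ANCOVA: V = 1 − ρ², with one error df fewer

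Example, n = 30 and ρ = 0.5: noncentrality is 30/6 = 5.00 for post-only and for change score (V = 1), and 30/(6 × 0.75) = 6.67 for ANCOVA. Power is 0.489 and 0.616.

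| n per arm | Post-only | Change score, ρ = 0.5 / 0.7 / 0.8 | ANCOVA, ρ = 0.5 / 0.7 / 0.8 | Gain over change, points |
|---|---|---|---|---|
| 20 | 0.337 | 0.337 / 0.526 / 0.712 | 0.435 / 0.599 / 0.759 | 10 / 7 / 5 |
| 30 | 0.489 | 0.489 / 0.720 / 0.885 | 0.616 / 0.793 / 0.917 | 13 / 7 / 3 |
| 50 | 0.727 | 0.727 / 0.921 / 0.987 | 0.849 / 0.957 / 0.993 | 12 / 4 / 1 |

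The ratio of ANCOVA to change-score variance is (1 − ρ²) / [2(1 − ρ)] = (1 + ρ)/2, that is 0.75, 0.85 and 0.90.

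**The case against.** The strongest reply is that the ANOVA sentence carries no time limit, and that the word for addition in the SAP's last paragraph suggests something wider came before it. The authors may have meant ANOVA for the outcomes too. The text leaves room for this, though the sentence follows directly on the baseline check and is most naturally part of it. The wider reading does not close the gap: it yields an ANOVA with no named outcome, visit, contrast, baseline term or multiplicity rule.

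A second reply is that the objectives speak of changes, which suggests that baseline would enter through change scores. That is fair as a guess at intent, but an objective is not a method. It does reduce the stakes: against change scores the advantage of ANCOVA can be as little as 1 to 3 points when ρ is 0.8.

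A third reply is that no single model is obligatory with four follow-up visits. That stands. What is essential is that outcome, visit, model and multiplicity rule are fixed in advance.

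Three stronger inferences are tempting, and the documents do not support them:

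- *The pre-intervention values serve only balance and masking.* They also serve the device-error calculation.
- *The trial will run with a false-positive rate near 80%.* That figure needs the less natural reading of the ANOVA sentence, an alpha that the plan never states, and independence between correlated outcomes.
- *The arms will be compared without baseline, or not at all.* The plan is silent; it does not say this.

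**Conclusion.** The point holds and should be fixed before outcome data are seen. As written, the SAP contains no analysis that answers the general objective or the third specific objective. This rests on the text alone and on no assumed number.

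The size of the consequence is less certain. About 28 to 32 outcome-by-visit results have no stated between-arm analysis, depending on whether algometry covers one side or two. This count treats the pain intensity of the second specific objective as pressure pain threshold, which the documents do not confirm. The error rates and the 1-to-13-point power gain over change scores are illustrations on assumed n, correlations, effect size and alpha; the verdict does not depend on them.

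**What to change.** Keep the baseline tables as description, and add an outcome analysis to the SAP before outcome data are seen:

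1. The sponsor names one primary outcome and one primary visit, and says whether pain intensity in the second specific objective means pressure pain threshold.
2. Primary model: ANCOVA at that visit with group and the pre-intervention value as covariate, subjects kept in the arm to which they were randomised. State which pre-intervention value is used, since there are two readings; their mean, taken the same way in all arms, is one choice.
3. Test the 2-df group effect at 5%, and make the three pairwise comparisons if it rejects. Report adjusted pairwise differences with 95% confidence intervals in every case.
4. Apply the same ANCOVA, with adjusted pairwise differences and 95% intervals, to the other outcomes and visits. Either make no significance claims there or state one multiplicity rule. Holm over the other six outcomes at the primary visit, tested only if the primary test rejects, is one option. In simulation (20 to 50 per arm) it held error across the seven 2-df tests at 2.2% to 5.1%. Counting the primary pairwise comparisons as well, error reached up to 9.5%, so the SAP should say that those are protected within the primary outcome only.

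A baseline-adjusted mixed model over the four post-intervention visits is an acceptable alternative or sensitivity analysis.

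**Cost.** SAP wording and slightly more analysis work, with no extra subjects, visits or measurements. Fewer secondary results will be nominally significant.

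**To be raised separately.** First, which trapezius side defines the homolateral and contralateral outcomes in the control arm, given that the evaluator is to "locate the Myofascial trigger point (MTP) 1 of the upper trapezius, both right and left". Second, the order of randomisation relative to trigger-point location and exclusion: the protocol can be read as randomising after baseline data collection, and the text should be reconciled.

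### Baseline tests are used to verify randomisation (chi-square and ANOVA) and to check evaluator masking (ANOVA only), and they support neither conclusion

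*Combined protocol and SAP*

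**What the plan says.** The Statistical Analysis Plan gives the baseline tests two purposes.

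- **Randomisation.** The SAP opens with: "To verify the correct randomization of the subjects to the intervention groups, a baseline homogeneity analysis". Qualitative variables get a chi-square test. For the others: "For the quantitative variables, mean values and standard deviation (SD) will be calculated and a variance analysis procedure (ANOVA) will be applied".
- **Masking.** The last paragraph says: "The pre-intervention response variables will also be evaluated in the three intervention groups, to check their homogeneity and correct masking of the evaluator". It names ANOVA as the method; chi-square is not mentioned there.

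No significance level or decision rule is given for either purpose.

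The Study Protocol Plan fixes the order of events around treatment: "Once the pre-intervention measurements have been made, the subject will go to the adjoining room to carry out the intervention". On who measures, it says: "In one of the rooms will be the evaluator to perform the measurements and collect the pre- and post-intervention values". The post-intervention readings are taken immediately, at 24 h, at 72 h and at 7 days.

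The timing of allocation is less clear. After the eligibility check the text says: "After the data collection, a randomization (Epidat V4.0) of the selected subjects will be carried out". The evaluation-room measurements are described after that sentence, but the data collection it refers to is not defined.

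The only other mention of masking is in the control-group technique, where the subject keeps the "head stuck in the hollow of the head of the stretcher throughout the technique to make a correct masking". That concerns the subject, not the evaluator.

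**The concern.** A statement that randomisation was verified, or that the evaluator was correctly masked, tells readers how far to trust the results. This plan would rest both statements on tests of data collected before treatment.

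For randomisation, such a test asks whether chance could explain an observed difference. With sound allocation, chance is the explanation by construction, so some significant results are expected. A non-significant result says little about how the sequence was generated or concealed.

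For masking, the readings most exposed to an evaluator who knows the arm are the four taken after treatment, and none of them enters the test. The documents contain no other check of evaluator masking.

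**Working it through.** The documents give no sample size, alpha, expected difference or correlation, so the plan has no figure of its own to reproduce. Steps 1 to 3 are illustrations on assumed inputs. Step 4 needs no arithmetic.

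**Inputs.** From the protocol: three arms, six cervical movements, algometry at the trigger point (located on both sides), weight and height. Assumed: alpha 0.05, 20 to 40 subjects per arm, a common correlation r of 0, 0.3 or 0.5 between measures, and a shift of 0.3 or 0.5 SD in one arm. The number of tests is also assumed, because the SAP does not list its explanatory variables: 7 (six movements plus one algometry value), 8 (algometry on both sides) or 10 (adding weight and height).

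**1. Chance flags under sound randomisation.** P(at least one significant) = 1 − 0.95^k for independent tests.

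| k | Independent | r = 0.3 | r = 0.5 |
|---|---|---|---|
| 7 | 1 − 0.698 = 0.302 | 0.278 | 0.239 |
| 8 | 1 − 0.663 = 0.337 | 0.302 | 0.256 |
| 10 | 1 − 0.599 = 0.401 | 0.353 | 0.296 |

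The correlated columns are simulated with 30 per arm.

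**2. One ANOVA, one arm shifted by d.** With means (0, 0, d) in SD units, the noncentrality is n × (2/3) × d². For d = 0.3 and n = 20 it is 20 × 0.667 × 0.09 = 1.2. A non-significant result multiplies the odds of such a shift by (1 − power)/0.95. A significant one multiplies them by power/0.05.

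| d | n per arm | Power | Odds multiplier, not significant | Odds multiplier, significant |
|---|---|---|---|---|
| 0.3 | 20 | 0.145 | 0.90 | 2.9 |
| 0.3 | 30 | 0.201 | 0.84 | 4.0 |
| 0.3 | 40 | 0.258 | 0.78 | 5.2 |
| 0.5 | 20 | 0.337 | 0.70 | 6.7 |
| 0.5 | 30 | 0.489 | 0.54 | 9.8 |
| 0.5 | 40 | 0.621 | 0.40 | 12.4 |

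**3. Seven ANOVAs read together, all seven measures shifted in one arm** (simulated, 20 to 40 per arm, r from 0 to 0.5).

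| Shift | P(at least one flag) | Odds multiplier, a flag | Odds multiplier, no flag |
|---|---|---|---|
| None | 0.23 to 0.30 | – | – |
| 0.3 SD | 0.48 to 0.88 | 2.0 to 2.9 | 0.18 to 0.68 |
| 0.5 SD | 0.76 to over 0.99 | 3.1 to 4.0 | below 0.01 to about 0.3 |

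A wholly clean table is therefore real evidence against a large shift in every measure. It is much weaker evidence against a modest shift in one measure.

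**4. Masking, by order of events.** The pre-intervention readings are finished, the subject goes to the adjoining room, treatment is given, the subject returns, and the four later readings follow. Any cue that arises from treatment onward comes after the tested values are fixed, so it cannot change them. For the baseline period there are two cases:

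- If allocation came after the readings, a baseline difference cannot reflect knowledge of the arm.
- If allocation came before, a difference could arise from an evaluator who already knew it, but chance produces the same pattern. It is a hint at most.

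**The case against.** The best defence is that these tests are customary and not empty. A gross imbalance can raise suspicion of subverted allocation. If allocation came first, a baseline difference could point to an evaluator who already knew the arm. On the assumed inputs, one significant ANOVA raises the odds of a 0.5 SD shift 7- to 12-fold, and seven clean tests lower the odds of a shift in every measure substantially. This stands, so it would be too strong to call the tests worthless. But raising or lowering suspicion does not verify randomisation or establish masking. A shift is also not the same thing as faulty allocation: concealment can fail and leave no visible imbalance.

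A second defence is that the SAP ties masking to pre-intervention values and never says that the test confirms masking at follow-up. That is fair. A reader might infer such a claim, but the text does not make it. The criticism is that an unqualified check of correct masking invites that reading, while masking at the later readings goes unchecked.

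Third, the separate rooms give the evaluator some protection. They do, but that is a design feature and not something the ANOVA shows.

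A reader might also infer that the evaluator will be unmasked by time away, since for one arm "the superficial dry needling technique will be performed with a duration of nine minutes in the upper trapezius" and the deep technique takes under a minute. The documents do not establish this. Total time away also includes undressing, a one-minute wait, haemostasis and dressing, and the control procedure's duration is not stated. It is a possible cue only.

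**Conclusion.** The point holds and is minor. Chi-square and ANOVA at baseline cannot verify the randomisation, and ANOVA on pre-intervention values cannot confirm evaluator masking, least of all at the four post-treatment readings. Both conclusions follow from the stated purposes and the order of events, and need none of the assumed figures.

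The size of the chance-flag problem, about 30% to 40% of sound trials, assumes alpha 0.05 and 7 to 10 independent tests. With correlations of 0.3 to 0.5 it falls to about 24% to 35%.

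No effect estimate or decision rule in the supplied text depends on these tests. The consequence is an unsupported validity claim, not a wrong treatment result. The documents give no ground for inferring that the randomisation is faulty, that the evaluator is in fact unmasked, or that the trial's comparisons are biased.

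**What to change.** **In the SAP**

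- Delete both stated purposes and the baseline p-values. Replacement text: *Baseline characteristics and pre-intervention values will be described by group as mean (SD) or n (%).*
- Adjust the between-group outcome comparison for the pre-intervention value whatever the observed balance. The SAP as supplied does not describe that comparison, so this belongs in its specification.
- Make no claim of verified randomisation or masking from baseline tests.

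**In the protocol**

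- Describe how the sequence is generated and how allocation is concealed. The software is named, but nothing further is said.
- State whether allocation comes before or after the pre-intervention measurements.
- State how the evaluator is kept unaware of allocation, including whether time away from the evaluation room is alike across arms.

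**Optional.** Have the evaluator record one guess (superficial, deep, control, don't know) after the last 7-day reading, and report guess by arm as a plain table without a test. The guess may reflect observed response, comes a week after any time-away cue, and describes unmasking without preventing it. Guesses by one evaluator are also not independent of each other.

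**Cost.** Wording only for the main change: the means and SDs are already planned and the pre-intervention values already collected. The optional guess adds one tick-box per subject at an existing visit.
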